4.1 Overall Design

This is a randomized, double-blind, placebo-controlled, nation-wide multi-center phase III clinical trial comparing the efficacy and safety of apatinib and placebo in the treatment of patients with advanced HCC. The overall design is shown in [Figure 4.1](#) below.

This trial plans to be carried out at multiple sites in China. The list of participating study centers is shown in Appendix 6. It is planned to enroll a total of 360 patients with advanced HCC. According to the resolution of scientific committee, additional subjects will be enrolled, i.e., 390 subjects in total, who will be randomly assigned to the treatment group and the placebo group in a 2:1 ratio.

If none of the following conditions occur, such as withdrawal of informed consent from by subject, unacceptable toxicity, or conditions rendering the subject not suitable for further trial participation based on the opinion of the investigator, the study treatment of each subject will be continued until confirmed radiographic progression. The efficacy and safety index should be monitored during the trial.

The 28-day follow-up is necessary after treatment discontinuation, and then the subjects will continue to be followed to gather information on their survival.

Figure 4.1. Overall design

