4.5.2 Dose

Treatment group: Apatinib, 750 mg, q.d.; The dose can be reduced according to toxicity, with the first reduction to 500 mg, q.d., and the second reduction to 250 mg, q.d.; each treatment cycle contains 28 days.

Placebo group: Placebo, q.d. Each treatment cycle contains 28 days.

Considerations for the use of 750 mg in the treatment group:

1. According to the phase I PK data, the C_{max} and AUC of the 850 mg group were both higher than those of the 750 mg group, and it was speculated that the toxicity of the 850 mg group might be higher than that of the 750 mg group;
2. According to the phase II study of apatinib in HCC, the efficacy of the 850 mg group was comparable to that of the 750 mg group (TTP, OS; the DCR in the 850 mg group was slightly higher than that in the 750 mg group); 9 patients in the 850 mg group withdrew from the study due to adverse events with the duration of treatment less than 1 cycle (including 4 cases of gastrointestinal hemorrhage), while 3 patients in the 750 mg group withdrew from the study due to adverse events with the duration of treatment less than 1 cycle (no hemorrhage). Considering that the primary endpoint of phase III trial is OS, the dose of 750 mg, which showed better tolerability in HCC patients, is selected for the study.

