7 CRITERIA FOR DOSE INTERRUPTION AND MODIFICATION

7.1 Dose Level and Use of Drugs

The dose levels in the treatment and placebo groups are: 1) starting dose: 750 mg, q.d.; 2) second dose level: 500 mg, q.d.; 3) third dose level: 250 mg, q.d. The initial dose of each group can be reduced by two levels. After dose reduction, the dose can be resumed to the previous dose level if the toxicity is completely recovered; if the dose is reduced again, no further modification is allowed. The administered doses and dose modification of each group are shown in the table below, and the dose can be modified according to the "Dose Modification" column shown below.

Table 8. Doses and dose level modification of each group

	Treatment Group	Placebo Group
Starting dose	■■■	□□□
First dose reduction	■■	□□
Dose re-modification Toxicity recovery ^a	■■■	□□□
Second dose reduction ^b	■■	□□
Third dose reduction	■	□
Dose re-modification Toxicity recovery ^a	■■	□□
Fourth dose reduction ^b	■	□

Note: ■ = Apatinib mesylate tablets 250 mg/tablet, □ = Apatinib mesylate dummy tablets

a After dose reduction, the dose can be resumed to the previous dose level if the toxicity is completely recovered;

b If the dose is reduced again, it should not be resumed again.

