7.2.3 Dose reduction

In each dosing cycle, only one dose reduction is allowed (i.e., the reduction of one dose level); after dose reduction, the dose can be resumed to the previous dose level after the toxicity has completely recovered; however, if the dose is reduced again, it should not be

resumed again. Each subject is only allowed up to two dose reductions, i.e., after the dose is reduced to the third dose level, the dose is not allowed to be resumed, but the dose can be interrupted.

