7.2.6 Discontinuation criteria based on liver function

1) If the subject has $ALT > 5 \times ULN$ and total bilirubin $> 2 \times ULN$, the following measures must be taken:

(1) Immediately discontinue the use of the investigational drug and give active symptomatic treatments;

(2) Complete the SAE form and handle it in accordance with the requirements for SAE in Section 11 of this protocol;

(3) Follow-up the event according to the requirements for "Follow-up of Adverse Events" in Section 4 of this protocol, and check liver function every week until it returns to the baseline level;

7.3 If the subject experiences any of the following conditions:

$ALT > 8 \times ULN$ or $ALT > 5 \times ULN$ for more than 2 weeks: The patient must be reexamined within 3 days after the first occurrence of the event, and then reexamined weekly to monitor whether the ALT value continues to increase. If the ALT value continues to increase, the use of the apatinib should be interrupted. The liver function should be reexamined within 2 weeks. If the treatment is effective and the subject is willing to continue to receive the apatinib treatment after obtaining the results of the liver function test, the subject can resume the apatinib treatment at the next lower dose level after obtaining the permission of the investigator and the medical director of the sponsor, and the liver function of the patient should be monitored every 2 weeks until it returns to the baseline level.

Other rules

To ensure the consistency of dose modifications throughout the study, treatment should be first discontinued before undergoing a dose modification for each dose cycle. The dose can only be reduced if the subject still cannot tolerate the dose after dose interruption.

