12.3 Statistical Analysis Plan

Time for efficacy analysis and safety assessment: Based on the full analysis set, when 312 deaths ($\geq 80\%$ of patients died) occur, a final verification of the data in eCRF shall be performed. After the data integrity is verified and all quality assurance (QA) and quality control (QC) procedures on the data management are performed, the randomization protocol must be disclosed, and the data from the clinical database will be retrieved to record and statistically analyze the efficacy and safety data. In the efficacy analysis, the data cutoff date is the date when the 312th death occurs. In the analysis of overall survival (OS), if the subject does not die at or before the cutoff date, and if there are data (study visits, survival follow-ups, etc.) confirming that the subject has died or is still alive after the cutoff date, the subject data will be reviewed on the cutoff date. If the last date of known survival of a subject is before or at the cutoff date, the data of the subject will be reviewed on the day of last known survival. In the analyses of progression-free survival (PFS) and time to disease progression (TTP), if the subject has neither disease progression events (for TTP and PFS) nor death (for PFS only) at or before the cutoff date, then the data of the subject will be reviewed on the subject's last day of radiographic tumor assessment on or before the cutoff date, except for the following case: For any radiographic tumor assessment as per the RECIST v1.1 criteria that indicates no evidence of progression, the review date will be set as the cutoff date.

Pre-set subgroup analysis: Subgroups will be pre-defined based on the following factors for a confirmatory subgroup analysis in this study: age \leq 65 years or $>$ 65 years; ECOG score 0 or 1; with or without vascular invasion; with or without extrahepatic metastases; with or without vascular invasion and extrahepatic metastases; positive or negative HBV; and with or without past history of sorafenib treatment.

All statistical analyses will be performed using SAS. All statistical analyses are performed using two-tailed tests. $P \leq 0.05$ is considered statistically significant, and 95% confidence is used for confidence intervals.

Analyses were performed as per groups based on the initial dose and the dose at the end of treatment, respectively.

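### Protocol 12.3 calls for analyses grouped by dose at the end of treatment, a post-randomization grouping whose survival comparison cannot be interpreted, and the SAP leaves it out without withdrawing it

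*Protocol*

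**What the plan says.** The instruction is one sentence in Protocol 12.3: "Analyses were performed as per groups based on the initial dose and the dose at the end of treatment, respectively". It stands after the data cutoff rules for OS, PFS and TTP and the two-sided 0.05 rule, and just before the analysis sets for efficacy and safety. It gives no endpoint, arm, reference group or method, and no landmark or time-dependent handling of dose.

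The dosing rules determine how end dose arises:

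- Both arms start at the same level (Protocol 7.1: "The dose levels in the treatment and placebo groups are: 1) starting dose: 750 mg, q.d.; 2) second dose level: 500 mg, q.d").
- A cycle lasts 28 days (4.5.2: "each treatment cycle contains 28 days"), and reductions are paced (7.2.3: "In each dosing cycle, only one dose reduction is allowed").
- Interruption comes before reduction (closing rules of 7.2.6: "The dose can only be reduced if the subject still cannot tolerate the dose after dose interruption").
- Re-escalation is possible (7.1: "After dose reduction, the dose can be resumed to the previous dose level if the toxicity is completely recovered").
- With the usual exceptions for toxicity, withdrawal of consent and investigator judgement, "the study treatment of each subject will be continued until confirmed radiographic progression" (4.1). Section 4.5.4 lets some patients continue beyond progression.

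The SAP does not take the analysis up. Efficacy is analysed by randomized group (6.1), and the primary test is a stratified log-rank test of the two arms (7.3.1). The 13 OS subgroup factors (7.6.1) and the OS sensitivity analyses (7.6.2) do not include end dose. Dose modification and intensity are only summarized (7.4.2, Appendix 3). Nowhere does the SAP say that the protocol sentence is withdrawn.

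**The concern.** Since everyone starts at the same level, only the end-dose half of the sentence adds anything, and it sorts patients by something that happens during follow-up. To be recorded at 500 mg a patient must be alive and on treatment when the reduction is made. To be recorded at 250 mg the patient must reach a second cycle as well. A patient who dies or progresses before any reduction is recorded at 750 mg. An OS analysis that starts the clock at randomization credits the guaranteed survival to the lower dose.

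Reductions are also triggered by toxicity, and toxicity may track frailty. That pulls the comparison the other way. A table of OS or PFS by end dose could therefore suggest a dose-response, or a benefit or harm of dose reduction, that does not exist.

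**Working it through.** **Reference scale.** The plan gives no figure for an end-dose analysis. Its design effect is HR = 6/8.5 = 0.706 (Protocol 4.3). The stated total of 331 is roughly reproduced: 292 events by Schoenfeld's formula at 2:1, divided by an event probability of 0.893, gives 327. At 2:1, 390 subjects put 390 × 2/3 = 260 on apatinib.

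**Inputs.**
- Median OS on apatinib is 8.5 months (Protocol 4.3), taken as exponential.
- Treatment stop other than death has a median of 3.3 months, the phase II median TTP at 750 mg (Protocol 1.5.7), varied from 2.0 to 5.0.
- At most one reduction per 28-day cycle (Protocol 7.2.3).
- Assumed, because the documents give no rate: reduction hazard 0.1, 0.2 or 0.4 per month.
- Dose has no effect on death.

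**Hand check of the mechanism (3.3 months, 0.2 per month).**
- Death hazard: ln 2/8.5 = 0.0815. Other stop: ln 2/3.3 = 0.2100. Reduction: 0.2000. Sum: 0.4916.
- Share reduced before stopping: 0.2000/0.4916 = 0.41, so 59% end at 750 mg.
- Mean time to the first of the three events: 1/0.4916 = 2.03 months, the same in both groups.
- Mean OS overall: 8.5/ln 2 = 12.26 months.
- Reduced patients are all alive at that first event, so their mean OS is 2.03 + 12.26 = 14.30 months (from unrounded terms).
- Of the unreduced, 0.0815/(0.0815 + 0.2100) = 0.28 are dead at that event, so their mean OS is 2.03 + 0.72 × 12.26 = 10.87 months.
- The gap of 3.43 months (0.28 × 12.26) arises with no dose effect. It comes entirely from assigning deaths before reduction to 750 mg.

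**Simulation, reductions unrelated to prognosis.**

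| Case | HR, any lower dose vs 750 mg | HR, 500 mg | HR, 250 mg |
|---|---|---|---|
| Central (3.3 months, 0.2/month) | 0.75 | 0.84 | 0.65 |
| Stop median 5.0 months, 0.1 to 0.4/month | 0.65 to 0.69 | 0.77 to 0.85 | 0.56 to 0.57 |
| Central with 30% re-escalation | 0.74 | 0.84 | 0.66 |

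In the central case the shares ending at 750/500/250 mg are 59/24/16%, with median OS 6.9, 9.0 and 13.0 months. With 260 patients, a falsely significant benefit appears in 63% of trials. Over all rates and stop times the HR for any lower dose is 0.65 to 0.83, and the false-positive rate is 19% to 88%.

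**Sensitivity to the OS-PFS relation.** If OS is built as PFS (median 3.3 months) plus an independent exponential tail, with median reduction time 2 or 4 months, the HRs are 0.40 / 0.39 for 250 mg and 0.74 / 0.69 for 500 mg. With the same reduction times but treatment stop independent of death, they are 0.66 / 0.66 and 0.87 / 0.83. The assumed structure, more than the reduction time, decides the size at 250 mg.

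**Sensitivity to frailty.** Here reductions cluster in Cycle 1 (0.8 per month, then 0.02). A normal frailty term raises the death and stop hazards (SD on the log scale) and the reduction hazard (coefficient g).

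| SD, g | HR, any lower dose | HR, 500 mg | HR, 250 mg |
|---|---|---|---|
| 0, 0 | 0.90 | 0.92 | 0.69 |
| 0.5, 0.3 | 0.98 | 1.01 | 0.67 |
| 0.5, 0.5 | 1.10 | 1.12 | 0.81 |
| 0.7, 0.7 | 1.24 | 1.27 | 0.88 |

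With a constant reduction rate of 0.2 per month, the same three frailty settings leave the HR for any lower dose at 0.69 to 0.75. Reversal therefore needs early reductions that also fall on frail patients.

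**A fixed landmark.** Classifying dose at 8 weeks among patients then alive gives HR 0.99 to 1.02 when reductions are unrelated to prognosis. With frailty-linked reductions it gives 1.09 to 1.61. A landmark removes the guaranteed-survival bias but not the confounding.

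**The case against.** The strongest reply is that the SAP already does the right thing: efficacy by randomized group, dose described only, and no OS subgroup or sensitivity analysis by dose. That stands, and it confines the defect to one unreconciled protocol sentence. It does not remove it. Following the protocol produces the misleading table, and following the SAP drops a protocol analysis without a record.

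A reader might infer three stronger things that the documents do not support.

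- **That lower end doses must look better.** Reductions are driven by toxicity, and one is allowed within Cycle 1, so ending at 500 mg needs little guaranteed survival. The frailty runs show the direction can change there.
- **That the protocol orders OS by end dose, or a low-dose-versus-placebo contrast.** The sentence names no endpoint. Including OS and PFS is a reading of its place in 12.3. No contrast of an end-dose group with placebo is specified, and placebo has the same dose levels.
- **That end dose cleanly measures time on treatment.** Re-escalation lets long-treated patients finish at 750 mg, and treatment beyond progression is possible. Both blur the sorting.

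It is also fair to object that an HR near 0.4 at 250 mg depends on one modelling choice. It is given only as the far end of a range.

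**Conclusion.** The concern holds in this limited form. Protocol 12.3 calls for a post-randomization grouping, does not exclude survival endpoints from it, and gives no method that would protect the comparison. With no dose effect and reductions unrelated to prognosis, the spurious OS effect for any lower dose is close in size to the design HR of 0.706. With early reductions in frailer patients it can disappear or reverse at 500 mg. Since neither the size nor the direction can be known in advance, the comparison is uninterpretable either way.

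Confidence in the mechanism is high and in the size moderate: time on treatment is a phase II proxy, and the other drivers are assumed. PFS was not simulated. The randomized primary OS comparison is untouched, so this is a minor point that should be corrected, not a threat to the trial's main conclusion.

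**What to change.** - In Protocol 12.3, delete the grouping by dose at the end of treatment for efficacy, and state that efficacy is analysed by randomized arm only.
- Keep end dose as a descriptive exposure summary alongside SAP 7.4.2 and Appendix 3.
- Add a sentence to the SAP recording that the protocol's end-dose analysis is withdrawn or limited to description. Do this before unblinding, because dropping it afterwards could look selective.
- If a dose-survival question is kept, prespecify a fixed landmark or a time-dependent dose covariate, label it exploratory, and state that confounding by toxicity and frailty remains.

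The cost is about one sentence in each document. No data collection, patient or dosing rule changes.

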13 DROPOUTS

All eligible subjects who have signed the informed consent form have the right to withdraw from the clinical trial at any time. Subjects who have not received 1 cycle of treatment and undergone safety and efficacy assessments are considered drop-outs, regardless of the time and reason for withdrawal (withdrawals due to clear medical evidence of progression are not drop-outs). After a subject drops out, the investigator must document the reason for the drop-out in the eCRF, complete all the assessments possible, and document the last visit in the eCRF. Any drop-outs due to adverse drug reactions, which are determined to be related to the investigational drug during follow-up, must be documented in the eCRF and the investigator must be notified. Subjects who have undergone screening but withdrawn without obtaining a medication number are not considered dropouts. When conducting the safety assessment, a statistical analysis should also be performed for subjects who complete an entire treatment cycle and have detailed documents available.

Subjects who withdraw are not permitted to be enrolled again, and the subjects' number may not be reused.

15 DISCUSSION, APPROVAL, AND AMENDMENT OF TRIAL PROTOCOL

The above "Clinical Study Protocol" and "Clinical Study Case Report Form" shall be formulated after discussion by the principal investigators of participating centers, approved by Jiangsu Hengrui Pharmaceuticals Co., Ltd., and implemented upon approval by the ethics committees of participating centers. During the clinical trial, any revisions to the protocol should be reported to the Ethics Committee for approval or filing.

16 LAWS, REGULATIONS AND ETHICS

Laws and Regulations

According to the requirements of relevant regulations in China, an application should be submitted to the NMPA to obtain a clinical trial approval number before starting a clinical trial of a new drug. The clinical trial approval number of this investigational drug, apatinib, is 2014L00877. Before the start of this trial, it should be approved or archived by relevant regulatory authorities. The clinical trial should also be implemented in compliance with all applicable regulatory requirements.

Ethical Standards

This clinical trial must comply with the "Declaration of Helsinki" (1996), NMPA's "Good Clinical Practice" (GCP)^[15], and related regulations.

Ethics Committee

This trial protocol must be reviewed and approved by the ethics committee of each site prior to implementation. During the review by the ethics committee, the sponsor and the investigator should provide the ethics committee with relevant clinical trial documents, including but not limited to: "Ethical Review Application", "Clinical Study Approval" from NMPA, "Clinical Study Letter of Authorization", "List of Clinical Trial Staff", "Certificate of Analysis of the Investigational Drug", "Sample Informed Consent Form", "Clinical Trial Protocol", "Case Report Form (CRF)", and "Investigator's Brochure" for clinicians. During the trial, revisions to this protocol must be reported to the ethics committee and put on record.

Confidentiality of Subject Information

In the course of this trial, a great effort will be made to protect the personal privacy of all subjects. The sponsor's forms, study reports, publications, and any other published materials must not include the name of subjects unless required by law. This trial will use highly confidential methods to transmit data in order to prevent the leakage of the personal data of the subjects.

17 TRIAL PROGRESS

The trial is expected to be carried out from November 2013 to March 2018.

18 TRIAL PROTOCOL COMPLIANCE

The investigator shall try his/her best to avoid protocol violations. At any time, the investigator should not contact Jiangsu Hengrui Pharmaceuticals Co., Ltd. and ask for approval of protocol violations, because any authorized protocol violation should never be allowed. If the investigator believed that a certain protocol deviation could improve the implementation of the trial, the investigator must consider protocol revisions. However, the revised protocol can only be implemented after it is approved by Jiangsu Hengrui Pharmaceuticals Co., Ltd. and the medical ethics committee. All major protocol violations should be recorded and reported on the clinical trial report.

Appendix 1. Response Evaluation Criteria in Solid Tumors RECIST Version 1.1.

1 MEASURABILITY OF TUMOR AT BASELINE

1.1 Definitions

At baseline, tumor lesions/lymph nodes will be categorized measurable or non-measurable as follows:

Measurable lesions

Tumor lesions: Must be accurately measured in at least one dimension (longest diameter is to be recorded) with a minimum size of:

- 10 mm by CT scan (CT scan slice thickness no greater than 5 mm)
- 10 mm caliper measurement by clinical exam (lesions which cannot be accurately measured with calipers should be recorded as non-measurable);
- 20 mm by chest X-ray
- Malignant lymph nodule: pathologically enlarged and measurable, single lymph nodule must be ≥ 15 mm in short axis by CT scan (CT scan slice thickness no greater than 5 mm). At baseline and during follow-up, only the short axis will be measured and followed.

Non-measurable lesions

All other lesions, including small lesions (longest diameter < 10 mm or pathological lymph nodule with ≥ 10 mm to < 15 mm short axis) as well as truly non-measurable lesions.

Non-measurable lesions include: meningeal disease, ascites, pleural or pericardial effusion, inflammatory breast cancer, lymphangitis carcinomatosa of the skin or lung, abdominal masses unable to be diagnosed or followed by imaging techniques, and cystic lesions.

Special considerations regarding lesion measurability

Bone lesions, cystic lesions, and lesions previously treated with local therapy require particular comment:

Bone lesions:

- Bone scan, PET scan or plain films are not considered adequate to measure bone lesions. However, these techniques can be used to confirm the presence or disappearance of bone lesions;
- Lytic lesions or mixed lytic-blastic lesions, with identifiable soft tissue components, that can be evaluated by tomography techniques such as CT or MRI can be considered as measurable lesions if the soft tissue component meets the definition of measurability described above;

- Blastic lesions are non-measurable.

Cystic lesions:

- Lesions that meet the criteria for radiographically defined simple cysts should not be considered as malignant lesions (neither measurable nor non-measurable) since they are, by definition, simple cysts.
- Cystic lesions thought to represent cystic metastases can be considered as measurable lesions, if they meet the definition of measurability described above. However, if noncystic lesions are present in the same patient, these are preferred for selection as target lesions.

Lesions with prior local treatment:

- Tumor lesions situated in a previously irradiated area, or in an area subjected to other locoregional therapy, are usually considered non-measurable unless there has been demonstrated progression in the lesion. Study protocols should detail the conditions under which such lesions would be considered measurable.

